# timing of final analysis at 804 total events or a maximum time of March 2022

11.3 Analysis of Secondary Endpoints

Secondary analyses will be performed for comparison between the two arms regarding survival and adverse events. With 732 patients on each arm, toxicity rates can be estimated to within at worst  $\pm 3.7\%$  (95% confidence interval). Additional exploratory analyses will include assessing the treatment effect within subgroups defined by the stratification factors as well as the interaction of everolimus with each of the stratification

factors, and whether the surgery was partial or a radical nephrectomy. With at least 15% of the patients having non-clear cell histology, for this subgroup the difference in the survival rates between the treatment arms can be estimated to within at worst  $\pm 5\%$  (95% confidence interval).

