We still assume an ideal HR=0.75, but we increase the accrual duration by one year to 4.5 years, and keep 4 years of follow-up. We are also reducing the statistical power from 85% to 80% in order to achieve a sample size that seems achievable within a reasonable amount of time. By making the prior assumptions about treatment efficacy, we will have an effective HR of 0.82 based on the proportion of dropouts and when they became noncompliant.

Assuming exponential recurrence-free survival, 4.5 years of patient accrual, four additional years of follow-up and an updated sample size of 1464 eligible patients (732 per arm), the study has 80% power to detect a 18% reduction in the hazard rate of recurrence free survival with everolimus compared to placebo (HR=0.82). This corresponds to an improvement in the median RFS from 4.9 to 6.0 years if the RFS distributions are exponential. We will use a one sided stratified log rank test with  $\alpha=0.025$ .

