## 11.2 Analysis of Primary Endpoint

This study's design is based on assumptions about the accrual rate, the distribution of intermediate-high and very-high risk patients that have been randomized on ASSURE and histology. The total projected accrual adjusted for a 5% ineligibility rate is 1,537 patients (previously 1,218). If accrual to the intermediate-high risk strata reaches 50% of the total projected accrual then the stratum will be closed to further accrual. If accrual to the clear cell histology stratum reaches 85% of the total projected accrual then the stratum will be closed to further accrual. This will ensure accrual patterns in the strata with high event rates are comparable to those assumed in the study design. If the event rate information becomes available from ASSURE, the study team may consider recommending that the sample size be reevaluated. The sample size adjustment would be based on baseline characteristics. Only the number of patients accrued would possibly change, but the number of events and formal analysis timepoints, which are based on number of events, would not change.

The first interim analysis will be conducted after approximately 1,000 patients have been entered ( $n=500$  per arm), approximately 4 years after the study opens and when 30% of the expected number of recurrences have occurred on the placebo arm. A second interim analysis will be conducted approximately 5 years after the study opens and when 50% of the expected events on the placebo arm have been observed. The third interim analysis will be conducted when 70% of the expected events on the placebo arm have been observed. The fourth interim analysis will occur approximately 7.5 years after study activation when 90% of the expected events on the placebo arm have been observed. For each interim analysis, timing of analysis will be based on percent of expected information and not on calendar time. Evidence suggesting early termination of the trial and a conclusion that everolimus is not better than placebo would be if the alternative hypothesis of a 22% improvement in recurrence-free survival with the experimental arm is rejected at the 0.002 level. In addition, the null hypothesis of no difference in recurrence-free survival will be tested at the one-sided level of 0.001. If the decision is to continue the study to completion, the final analysis will be done after complete accrual

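### Section 11.3 states ±5% worst-case 95% precision for the between-arm survival difference in non-clear-cell patients; the plan's own numbers give about ±13%

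*Combined protocol and SAP*

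**What the plan says.** Section 11.3 makes two precision statements.

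- The first is for adverse events: "With 732 patients on each arm, toxicity rates can be estimated to within at worst" ±3.7%, as a 95% confidence interval.
- The second is for the histology subgroup. It begins "With at least 15% of the patients having non-clear cell histology" and continues that "for this subgroup the difference in the survival rates between the treatment arms can be estimated to within at worst" ±5%, again as a 95% confidence interval.

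Between the two, the plan gives the status of the subgroup work: "Additional exploratory analyses will include assessing the treatment effect within subgroups defined by the stratification factors".

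The inputs come from the sections just before. The July 2015 revision in Section 11.1 sets 1,464 eligible patients, 732 per arm. In Section 11.2, "The total projected accrual adjusted for a 5% ineligibility rate is 1,537 patients". The same section supplies the 15% floor: "If accrual to the clear cell histology stratum reaches 85% of the total projected accrual then the stratum will be closed to further accrual". Histology is a stratification factor in Section 6.0, so the subgroup should split about evenly between arms.

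**The concern.** A subgroup that may be only 15% of the trial is given an interval for a difference between arms that is hardly wider than the interval quoted for a single toxicity rate in a whole arm. That cannot be right. A difference between two equal arms has √2 times the half-width of a single rate, and cutting the sample to 15% multiplies the half-width by a further 1/√0.15, about 2.6.

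Non-clear-cell patients are not an incidental subgroup. The study rationale in Section 2.0 points to possible particular activity of mTOR inhibition there and commits to closing the clear-cell stratum if needed to secure enough of them. The ±5% is the only precision the plan states for the treatment comparison in that group. Taken at face value, it implies that a survival difference of 7 or 8 percentage points could be told apart from zero. In the worst case such a difference lies well inside the real interval.

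**Working it through.** **Inputs**

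- Eligible patients: 1,464, 732 per arm (Section 11.1).
- Projected accrual: 1,537 (Section 11.2).
- Non-clear-cell share: 15% as the floor (Sections 11.2 and 11.3).
- Confidence level: 95%, z = 1.96. The worst case for a proportion is p = 0.5.
- Assumptions: an even split of the subgroup between arms, and no censoring before the time point.

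**Step 1: check the method on the toxicity figure.** For one arm, half-width = z × sqrt(0.25/n).

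- z = 1.96: 1.96 × sqrt(0.25/732) = 3.62%.
- z = 2: 2 × sqrt(0.25/732) = 3.70%.

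The stated ±3.7% therefore follows from the p = 0.5 method, with z rounded to 2. A 0.5/n continuity correction at z = 1.96 gives 3.69%, which also fits.

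**Step 2: apply the same method to the subgroup difference.** Per arm, n = 0.15 × 1,464 / 2 = 109.8. Half-width = z × sqrt(0.25/n + 0.25/n) = z × sqrt(0.5/n).

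- z = 1.96: 1.96 × sqrt(0.5/109.8) = 1.96 × 0.0675 = 13.2%.
- z = 2: 13.5%.

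Ratio to the stated figure: 13.2 / 5 = 2.6.

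**Step 3: try 15% of each sample size in the documents (z = 1.96).**

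| Total | Non-clear cell per arm | Half-width |
|---|---|---|
| 1,537 | 115.3 | 12.9% |
| 1,464 | 109.8 | 13.2% |
| 1,218 (superseded) | 91.35 | 14.5% |
| 1,170 (superseded) | 87.75 | 14.8% |

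**Step 4: try other readings at 109.8 per arm.**

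- Single-arm rate in the subgroup: 1.96 × sqrt(0.25/109.8) = 9.4%.
- One rate with both arms pooled: 1.96 × sqrt(0.25/219.6) = 6.6%.
- One standard error of the difference: sqrt(0.5/109.8) = 6.7%.
- One standard error of a single arm: sqrt(0.25/109.8) = 4.8%. This is near 5%, but it is neither a 95% interval nor a difference.

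**Step 5: try milder rates than one half.** The documents give no overall survival rate, so these are assumptions. With the same rate in both arms, 80% gives 10.6% and 90% gives 7.9%; 5% is reached only at about 96%. The plan's own recurrence-free survival assumptions (exponential, hazard ratio 0.82) give at 5 years:

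- control median 4.9 years: 49.3% against 56.0%, half-width 13.2%;
- control median 6.75 years: 59.8% against 65.6%, half-width 12.8%.

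At 1 year the same two assumptions still give 8.6% and 7.5%.

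**Step 6: what ±5% would mean or need.**

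- Confidence level at 109.8 per arm and p = 0.5: 2Φ(0.05/0.0675) − 1 = 54%.
- Patients per arm for a worst-case ±5%: 0.5 × 1.96² / 0.05² = 768.
- Whole-trial difference, for comparison: 1.96 × sqrt(0.5/732) = 5.1%, or 5.0% with the 1,537 split evenly.

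**The case against.** The arithmetic itself is hard to dispute. The best counter-arguments concern what the authors meant and how much it matters.

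- **The figure fits the whole trial.** A difference across all patients has a worst-case half-width of 5.0% to 5.1%, so a correct full-trial figure may have been attached to the wrong population. This is plausible, but it is an inference, because the plan shows no derivation. The sentence names the subgroup, so it remains wrong as written.
- **A digit may have been lost.** On the superseded 1,170 patients the half-width is 14.8%, which rounds to 15%, and Section 11.4 still tabulates against 1,170. This cannot be excluded from the text, but nothing supports it. Either way, the printed figure needs correcting.
- **The replacement depends on the convention.** The toxicity figure matches z = 2 or a continuity correction better than plain z = 1.96. With z = 2 the subgroup figure is 13.5%; with a continuity correction (adding 1/109.8 to 13.2%) it is 14.1%. This stands as a matter of rounding and does not bring the figure near 5%.
- **The share may exceed 15%.** A larger share would narrow the interval, but the worst case refers to the floor. Even if all 1,464 patients were non-clear cell, the half-width would be 5.1%.
- **Nothing depends on it.** This is largely right. The analyses are labelled exploratory, and nothing in the documents shows anyone relying on the figure. It limits the severity but does not remove the error.

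**Conclusion.** The stated ±5% is wrong for the population it describes. On the current sample size the worst-case 95% half-width is about 13% (13.2% on 1,464 eligible patients, 12.9% on 1,537), about 2.6 times the stated value. No 95% interval for the subgroup difference at the 15% floor comes to 5% under the worst-case condition the sentence sets.

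The result assumes an even split of the subgroup between arms and simple binomial rates. Loss to censoring before the time point would make the precision worse than 13%. Severity is minor: the error misstates the precision of one exploratory comparison and leaves the primary test, alpha, power, event target, stopping rules and the 85% clear-cell closure rule untouched.

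**What to change.** In Section 11.3, replace ±5% with about ±13%, and add that this rests on about 110 non-clear-cell patients per arm and is before any allowance for censoring. If the authors meant ±5% to describe the whole-trial difference, the sentence should say so and still give about ±13% for the subgroup.

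The cost is one figure in one sentence. Sample size, alpha, analysis timing and the analyses themselves do not change.

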#### 11.4 Analysis of Translational Medicine Endpoints

(A) Prognostic significance: Proportional hazards regression will be used to evaluate the association between genes and pathways and recurrence-free survival and overall survival. Additional exploratory methodology may include classification and regression trees or logic regression to identify combinations of markers that may be associated with the endpoints of interest. The following table shows the minimally detectable RFS hazard ratio for various prevalence of markers and rates of sample submission with 80% statistical power and a two-sided  $\alpha=0.05$ . This table assumes no treatment by marker interaction, and a median RFS of 4.9 years in those with the biomarker of interest.

Minimally Detectable Hazard Ratios for Recurrence-Free Survival

	sample submission (n=1170)	sample submission (n=936)	sample submission (n=702)
10% prev of a SNP	1.46	1.52	1.63
20% prev. of a SNP	1.33	1.38	1.45
30% prev. of a SNP	1.28	1.32	1.38

(B) Predictive significance: In order to evaluate whether molecular biomarkers in the AKT/mTOR pathway are predictive factors for everolimus, we will assess the interaction of the biomarker with treatment in a proportional hazards regression model assessing RFS. The entry in the following table is the minimally detectable ratio of the HR's of placebo/everolimus for those without the pathway activation relative to those that do have the activation. For simplicity of calculations, we assume that there is no prognostic association of biomarker activation and RFS in the placebo group, and the treatment effect for those without activation is null. That is, everolimus only has an impact on RFS among those with marker activation.

Minimally Detectable Interaction for Recurrence-Free Survival

Table entry is the hazard ratio of (Everolimus/Placebo) for those without marker activation relative to the HR of (Ever/PI) for those with marker activation, assuming 80% statistical power and a two-sided $\alpha=0.05$			
	100% sample submission	80% sample submission	60% sample submission
10% prev. of a marker	2.40	2.75	3.49
20% prev. of a marker	1.85	2.00	2.28
30% prev. of a marker	1.68	1.80	1.99

If 936 of patients randomized to this trial provide a usable tissue sample for these translational objectives, and the prevalence of the biomarker of interest is 20%, then we will have reasonable power (80%) to detect a hazard ratio of approximately 0.50 for those with a marker compared to a HR of 1.0 for those without the marker ( $1.0/0.50 = 2.00$ ). Frequency and severity of adverse events and proximity to sample collection will be correlated with steady-state  $C_{min}$ . Assuming 90% of those randomized to everolimus will submit one or more serum samples, we will have approximately 526 subjects to analyze.

Initially, correlations of adverse events and the  $C_{min}$  in closest proximity to the adverse event will be explored in a manner analogous to multiple t-tests. Logistic regression modeling will be used to assess whether  $C_{min}$  is a predictor for the presence of the adverse events after adjusting for other patient and disease covariates. Proportional odds (PO) models may be used to model severity of an adverse event in ordinal categories, if the PO modeling assumption is supported by the data.

#### 11.5 Pharmacokinetic Analysis of Blood Samples

For the pharmacokinetic analysis of blood samples, we will use blood samples that were collected at Week 7 or Week 13 and the patient must have been randomized to the everolimus arm and be receiving protocol treatment at the time of the blood draw. At the time of the on-study analysis in the winter of 2014, there were 83 patients with one blood draw and 165 with two for a total of 248 patients. For those with two on-treatment measurements, the average of the two will be used for analysis to reduce measurement error bias.

The purpose of the analysis is to correlate everolimus blood concentrations from early blood draws with the experience of adverse events by the patients, both in terms of general grades of toxicities but also by specific adverse events that have been more frequently reported on the everolimus arm. The following calculations assume a PK analysis will be conducted prior to accrual completion in order to gain insight into the relationship between blood levels of the study drug and adverse events. We anticipate there will be more samples to evaluate later in the trial and so effect sizes will be smaller with larger sample sizes.

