#### Most Prevalent Grade 2-4 Adverse Events in the Everolimus Arm of EVEREST

Among all Randomized Patients on the Everolimus Arm Who Received Any Study Drug

Toxicity	% of Evaluable with Grade 2-4
High Cholesterol	10%
Fatigue	19%
Hyperglycemia	14%
Hypertriglyceridemia	27%
Oral mucositis	35%
Rash	14%
Composite Endpoints	
Any Toxicity Grade 2-4	87%
Any Toxicity Grade 3-4	46%
Refusal/Tox within first 3 months	25%
Refusal/Tox within first 6 months	41%
Refusal/Tox prior to 12 months	52%

In order to simplify power calculations related to everolimus blood concentrations, we will assume the distribution of values will be divided into quartiles. The following table indicates the minimally detectable odds ratio that could be detected between the lowest and highest quartile in terms of predicting an adverse event. A range of prevalences are illustrated below to show how the effect size changes with the prevalence of the adverse event.

Minimally Detectable Odds Ratio for Highest versus Lowest Quartile of everolimus in the blood, assuming 80% Statistical Power and a Two-sided Alpha=0.05.

	Prevalence of Adverse Event Endpoint				
	10%	20%	30%	40%	50%

Q4 vs. Q1 of everolimus concentration	6.5	3.6	3.0	2.7	2.7
---------------------------------------	-----	-----	-----	-----	-----

An individual adverse event that is only reported by 10% of patients who receive everolimus will need to have a very strong association with concentration of everolimus in the blood (odds ratio 6.5 between highest and lowest concentration) in order to be detected as a significant association. An association of any Grade 3-4 toxicity only needs to be in the range of an odds ratio of 2.7 to be detectable.

For patients who have had a dose reduction of protocol therapy at the time of their blood draw, we will handle this in two ways. First, we will just analyze the everolimus level as it appears in the blood and ignore the dose received, and the second approach will standardize the amount of everolimus in the blood conditional on the dose of drug taken.

Logistic regression will be used to model adverse event outcomes with everolimus blood concentration as a predictor, adjusting for other stratification factors and age, gender and race.

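### Section 11.5 lists stopping drug within 3 months as a PK endpoint, but its analysis set largely excludes patients who could have that event, so the listed 25% does not apply to it

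*Combined protocol and SAP*

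**What the plan says.** Section 11.5 of the combined protocol and SAP defines the PK analysis set by two conditions. On timing: "we will use blood samples that were collected at Week 7 or Week 13". On treatment status: "the patient must have been randomized to the everolimus arm and be receiving protocol treatment at the time of the blood draw". At the winter 2014 analysis the set held "83 patients with one blood draw and 165 with two for a total of 248 patients". When both levels exist, "the average of the two will be used for analysis to reduce measurement error bias".

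The section then tabulates outcomes. Under composite endpoints it lists "Refusal/Tox within first 3 months" at 25%, followed by stops within 6 months (41%) and before 12 months (52%). The table heading gives the denominator: "Among all Randomized Patients on the Everolimus Arm Who Received Any Study Drug".

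For power, "we will assume the distribution of values will be divided into quartiles". Minimally detectable odds ratios for the highest versus lowest quartile are 6.5, 3.6, 3.0, 2.7 and 2.7 at prevalences of 10, 20, 30, 40 and 50% (80% power, two-sided 0.05).

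For patients with a dose reduction by the time of the draw, the section plans two analyses: one uses the level as measured, the other standardises it for dose. It sets no landmark time and no rule that an outcome must follow the draw.

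**The concern.** Membership of the analysis set depends on still taking the drug, and the 3-month endpoint is defined by no longer taking it. Patients who stop earliest have no qualifying level, and patients with a Week 13 level have almost run out of time to be 3-month stops. The 25% comes from all treated patients, so it is not the prevalence among those sampled.

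The averaging rule adds a second problem. Whether a patient's exposure is one value or the mean of two depends partly on whether the patient stopped, so exposure is not fixed before the outcome.

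At stake is the reading of one exploratory result. A null finding for the 3-month endpoint could be taken as evidence against a link between level and stopping when the analysis had much less power than the table suggests at 25%. A modest non-null odds ratio could come from how exposure was built.

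**Working it through.** **Inputs.** From Section 11.5: 248 patients (83 with one draw, 165 with two), so 248/4 = 62 per quartile; 80% power; two-sided 0.05; listed prevalences 25%, 41% and 52%. From Section 7.2: six-week cycles, so Week 7 starts on day 43 and Week 13 on day 85. Three months is taken as 13 weeks (91 days).

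**Step 1: reproduce the table.** Let the risks in the four quartiles follow a linear logit whose mean equals the stated prevalence, with a and b the risks in the lowest and highest quartiles. Solve

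Φ( (b − a) / √[(a(1−a) + b(1−b))/62] − 1.96 ) = 0.80.

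| Prevalence | 10% | 20% | 30% | 40% | 50% |
|---|---|---|---|---|---|
| Plan | 6.5 | 3.6 | 3.0 | 2.7 | 2.7 |
| Unpooled variance | 6.39 | 3.62 | 3.00 | 2.77 | 2.71 |
| Pooled variance | 6.73 | 3.73 | 3.08 | 2.83 | 2.77 |

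The table reproduces as a comparison of 62 with 62. Ranges below run from unpooled to pooled.

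**Step 2: read it at the listed 25%.** The solution is a = 0.150 and b = 0.364, an odds ratio of (0.364/0.636)/(0.150/0.850) = 3.23; the pooled version gives 3.32.

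**Step 3: what the schedule implies.** An on-treatment Week 13 sample means 84 days completed, which leaves about 7 days for a 3-month stop. If the 165 two-draw patients (67%) contribute almost none, a 25% prevalence needs 0.25 × 248 = 62 events among the 83 one-draw patients, or 75% of them. If 20%, 33% or 50% of one-draw patients are 3-month stops, prevalence in the set is 6.7%, 11.0% or 16.7%, and the detectable odds ratio is about 11.6-12.6, 5.7-6.0 or 4.0-4.2.

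**Step 4: vary the share lost before Week 7.** Let s be the share of 3-month stops before the Week 7 draw. The documents do not give s, so it is an assumption; 46% is 6/13, for stops spread evenly over 13 weeks. Assume also that sampled patients resemble all patients on drug at Week 7. Then

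prevalence = 0.25(1 − s)/(1 − 0.25s).

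| s | Prevalence | Events in 248 | Detectable OR | Power at OR 3.3 |
|---|---|---|---|---|
| 0 | 25% | 62 | 3.2-3.3 | 0.80-0.81 |
| 25% | 20% | 50 | 3.6-3.7 | 0.72-0.74 |
| 46% | 15% | 38 | 4.3-4.5 | 0.63-0.64 |
| 67% | 10% | 25 | 6.4-6.7 | 0.47-0.48 |

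**Step 5: the later endpoints.** At s = 46%, the excluded share of treated patients is 0.25 × 0.46 = 0.115. The 6-month prevalence becomes (0.41 − 0.115)/0.885 = 33%, and the 12-month prevalence (0.52 − 0.115)/0.885 = 46%. Detectable odds ratios are about 2.9-3.0 and 2.7-2.8, against about 2.8 and 2.7-2.8 at the listed values.

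**Step 6: the averaging rule with no true link.** Simulated levels were log-normal (between-patient CV 40-60%, within-patient variation 30%), with 15% of patients stopping independently of level. Stoppers have the Week 7 level only; stayers have the mean of two. These settings are assumptions.

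| Exposure used | Q4 vs Q1 odds ratio (truth 1.0) |
|---|---|
| Average, dose ignored, 20-30% of stayers halved between draws | about 1.15-1.4 |
| Average, dose-standardised | about 0.9 |
| Week 7 level only | 1.0 |

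The 0.9 arises because a mean of two right-skewed values is less variable and has a higher median than a single value, so single-value stoppers are over-represented in the lowest quartile.

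**The case against.** The strongest reply is that the section's stated purpose is to relate levels to adverse events. It applies the odds-ratio table in words only to a 10% adverse event and to any Grade 3-4 toxicity, and never quotes a detectable odds ratio for 3-month stopping. The table is indexed by prevalence and holds at whatever prevalence the sampled set has, down to 10%. The analysis is exploratory and has no part in the primary test or interim monitoring. All of this stands, and it limits the severity. It does not remove the point: the stops are labelled as endpoints, with prevalences from another population, directly above the power table.

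Four stronger readings are tempting, and the documents do not support them.

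- *The detectable odds ratios are invalid.* They reproduce; only reading the 3-month endpoint at 25% fails.
- *Averaging produces a false positive link.* That holds only in the planned analysis that ignores dose. The planned dose-standardised analysis removes that part and leaves a small distortion the other way.
- *Selection is known to weaken the link between level and stopping.* Neither the documents nor the working above establishes its direction.
- *This analysis is meant to explain the trial's early stopping.* Section 11.5 gives adverse events as its purpose.

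**Conclusion.** The point holds for the 3-month stopping endpoint. That the 25% describes a different population, and that two-draw patients can hardly have the event, follow from the text and the visit schedule alone. The size of the power loss rests on an unknown share of stops before Week 7: over 25% to 67%, the detectable odds ratio is about 3.6 to 6.7, against 3.2-3.3 at the listed prevalence. The averaging distortion is modest, about 0.9 to 1.4 under the simulated settings, and its direction depends on how dose is handled. The 6- and 12-month endpoints lose little power, although the averaging rule applies to them as well. Severity is low: one exploratory endpoint needs a better-matched method, and no confirmatory conclusion is affected.

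**What to change.** For the stopping endpoints, set a landmark at the Week 7 draw. Include patients on everolimus at that draw, use the Week 7 level only, and analyse time from the draw to a stop for refusal or toxicity in a time-to-event model with the covariates already planned (stratification factors, age, gender, race). Drop the 3-month stop from the logistic endpoints. Restate prevalence and detectable effect for patients on drug at Week 7; the actual number of 3-month stops among them replaces the assumption in Step 4. Keep the two-draw average for the other adverse event endpoints.

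The cost is SAP wording and a recalculated power line, with no new samples. The downsides are that the stopping endpoints lose the reduction in measurement error from averaging, patients with only a Week 13 sample drop out of them (their number is not given), and the stated detectable effects become less favourable.
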